## 4.3.2. Handling of Subject Withdrawals or Terminations

If a subject is withdrawn or discontinued from the study, the reason for withdrawal from the study must be recorded in the source documents and on the case report form. All subjects withdrawn prior to completing the study should be encouraged to complete study procedures scheduled for the Visit 5 / end of treatment (EOT) (Day 29) visit as soon as possible. All AEs should be followed as described in Section 7. Subjects who discontinue or are withdrawn from the study will not be replaced. Whenever a subject is discontinued prematurely, the Sponsor and the Medical Monitor must be notified.

## 4.4. Concomitant Medications

Subjects will be provided with calcium and vitamin D supplements to be administered daily from the Pretreatment Period until the end of the Treatment Period. The supplement dose will be determined by the Investigator and agreed by the Sponsor Medical Monitor, according to the subject's need to ensure that their daily intake of calcium and vitamin D is 1,200 mg/day and 800 IU/day, respectively. The doses and schedule of calcium and vitamin D supplements should be adhered to and not be changed other than for medical necessity. The supplements should be taken as instructed by the Investigator.

For any required concomitant medication, such as statins or antihypertensives, the subject must be on a stable dose for 90 days prior to the first treatment visit (Day 1) and every effort should be made to maintain a stable dose during study participation.

The occasional use of over-the-counter medications at approved doses (eg, ibuprofen or acetaminophen) for headache or minor discomfort is allowed. These are to be recorded on the appropriate case report form. Subjects should not take any other medications, including over-the-counter medications, herbal medications, or mega-doses of vitamins during the study without the prior approval of the Investigator.

If it becomes necessary for a subject to take any other medication during the study, the specific medication(s) and indication(s) must be discussed with the Investigator. All concomitant medications taken during the course of the study must be recorded in the subject's medical record or source document and transcribed into the eCRF.

## 4.5. Prohibited Medications

Please refer to Section 4.2 for medication related exclusion criteria.

Subjects should not take any other medications, including over-the-counter medications, herbal medications, or mega-doses of vitamins during the study without prior approval of the Investigator. The occasional use of over-the-counter medications (eg, ibuprofen or acetaminophen) for headache or minor discomfort will be allowed if discussed with the Investigator, recorded in the source documents, and in the subject's eCRF.

Use of corticosteroids for seasonal allergies or asthma is not prohibited. Use of low dose oral corticosteroids (eg,  $\leq$  5mg/day of prednisone or the relative equivalent dose of another corticosteroid) is also not exclusionary. Subjects who require chronic treatment with either an anticonvulsant (phenobarbital, phenytoin, carbamazepine or primidone), or with heparin will be discontinued.

## 4.6. Premature Termination or Suspension of Study

This study may be temporarily suspended or prematurely terminated if there is sufficient reasonable cause. Written notification documenting the reason for study suspension or termination will be provided by the suspending or terminating party to the principal investigator, and regulatory authorities. If the study is prematurely terminated or suspended, the principal investigator will promptly inform the Institutional Review Board (IRB) and will provide the reason(s) for the termination or suspension.

Circumstances that may warrant termination or suspension include, but are not limited to:

- Determination of unexpected, significant, or unacceptable risk to subjects.
- Insufficient compliance with protocol requirements.
- Data that are not sufficiently complete and/or evaluable.
- Decision of Sponsor.

Study may resume once concerns about safety, protocol compliance or data quality are addressed and satisfy the Sponsor, IRB and/or Regulatory Agencies, if applicable.

## 4.7. Temporary Suspension of Treatment

Due to the short nature of the study, temporary suspension of treatment is not an option for the Investigator. Any subject that is deemed inappropriate for continuing treatment will be withdrawn from the study and the reason will be noted in the CRF.

## 5. STUDY DRUG ADMINISTRATION AND MANAGEMENT

## 5.1. Study Medication

All study medications are for investigational use only and are to be used only within the context of this study, and administration of treatment is to be carried out as described in Section 5.5. Abaloparatide-sMTS will be supplied to the study site by RADIUS.

## 5.1.1. Abaloparatide-sMTS

The abaloparatide-sMTS is enclosed in a collar assembly for loading onto a spring-loaded applicator. The abaloparatide-sMTS dose will be 300 µg.

Abaloparatide-sMTS is stored refrigerated at 2° to 8°C (36° to 46°F). The abaloparatide-sMTS will be removed from refrigeration approximately 1 hour prior to application. Please refer to the pharmacy manual for further details.

## 5.2. Packaging, Labeling and Storage

## 5.2.1. Packaging and Labeling

Abaloparatide-sMTS and applicators will be supplied to the study site by RADIUS. All packaging operations will be performed in accordance with Good Manufacturing Practices.

All study drugs will be labeled with a caution statement and other information required by local Regulatory Authorities.

## **5.2.2. Storage**

All study medications (abaloparatide-sMTS) must be kept in a secure, limited-access storage area at 2° to 8°C (36° to 46°F) until dispensed for dosing or until returned to the Sponsor.

For Day 1 (Visit 3), Day 15 (Visit 4) and Day 29 (Visit 5/EOT), when the product is applied during a clinic visit, the used arrays will be carefully placed in a supplied container using minimal manipulation and frozen for returning to the manufacturer for further inspection and analysis according to a supplied handling procedure manual. Refer to the pharmacy manual for additional details.

Calcium and vitamin D supplements should be stored according to the manufacturer recommendations on the bottle.

## **5.3.** Study Medication Administration

Subjects will be encouraged to drink 8 ounces of water 1 to 2 hours prior to dosing.

Prior to the administration of study drug, the application site will be prepped and cleaned with an alcohol wipe, allowed to air dry, and then examined in order to assure that the area is not compromised. Each application site will be graded according to a 4-point scale by the investigator to assess signs of local skin reactions (at clinic visits; Section 6.6.2.1) and by the subject to assess symptoms of local skin reactions (each day during the treatment period; Section 6.6.2.2), prior to abaloparatide-sMTS application, immediately after removal of abaloparatide-sMTS, and at 1 hour after abaloparatide-sMTS application. For any severe local skin reactions, evaluations by the

subject will continue at 24 hour intervals until the reaction has stabilized or resolved (see Section 6.6.2.2).

Before initial use of abaloparatide-sMTS, the subject will be trained on the Instructions for Use and will demonstrate their ability to self-administer the abaloparatide-sMTS with the Investigator present. During subsequent applications, the subject will follow the Instructions for Use. It is important to note that if any component is damaged, the subject is to be instructed to replace the abaloparatide-sMTS patch with a new one and place the damaged patch in a container that was provided and to bring this together with the other used and unused abaloparatide-sMTS at the next clinic visit. Please refer to the pharmacy manual for additional details.

## 5.4. Treatment Assignment

All subjects who sign informed consent and continue to meet eligibility criteria for the study will be treated with abaloparatide-sMTS.

## 5.5. Dosing and Administration

The first self-administration of abaloparatide-sMTS will occur at the study site on Day 1, under observation.

Subjects will be trained by study personnel to self-administer study medication with the abaloparatide-sMTS patch and applicator; a single daily dose of 300 µg of abaloparatide-sMTS will be applied to the thigh for 5 minutes during the treatment period following the Instructions for Use. Please refer to the pharmacy manual for additional details on study drug administration.

The subject is to remain under observation for a minimum of 60 minutes after abaloparatide-sMTS. On the days when blood sampling is required after study medication administration, the subject is to remain at the vicinity of the clinic for the blood collections scheduled up to 4 hours after abaloparatide-sMTS application. Subjects are to be instructed to self-administer abaloparatide-sMTS application at a location where they have the ability to sit or lie down.

At each clinic visit during the Treatment Period, any used and unused abaloparatide-sMTS should be returned.

## 5.6. Treatment Compliance

To ensure treatment compliance, the Investigator or designee will supervise all study drug administration that occurs at the site. At each study visit, the Investigator or designee will review subject compliance with study drug administration and will remind the subject of study drug dosing requirements.

Subject compliance will be ascertained by using the data entered on the subject diaries as well as the total used and unused abaloparatide-sMTS returned at each study visit.

Discrepancies will be discussed with the subjects, documented in the medical charts, and recorded in the eCRF as appropriate. If a subject does not take the required medication or supplements (abaloparatide-sMTS, calcium and vitamin D), the reason for the missed dose is to be recorded by the subject in the subject diary.

## 5.7. Drug Accountability

The Investigator or designated site staff will maintain records documenting the dates and amounts of the following:

- Study drug received at the study site
- Study drug dispensed to the subject
- Study drug returned by the subject
- Study drug returned to sponsor/designee or destruction of study drug on site

Subjects will be provided with a container and instructed to return all used and unused study drug to the site for destruction. Study drug will be retained at the site until inventoried by the study monitor and approved for destruction or return. The study monitor will verify study drug records and inventory throughout the study.

## 6. STUDY PROCEDURES AND SCHEDULE

## **6.1.** Study Procedures

## **6.1.1.** Study Specific Procedures

The study-specific assessments are detailed in this section and outlined in Table 1. At Screening, any results falling outside of the reference ranges may be repeated 1 time at the discretion of the Investigator.

## 6.2. Study Schedule

This study is comprised of 5 clinic visits with either a sixth visit or telephone call for Follow-up. Study assessments are to be performed according to the SOA (Table 1). There is a  $\pm$  2-day window for each clinic visit.

The study will consist of a Screening (up to 2 months), a Pre-treatment Period (1 week), a Treatment Period (29 days) and a Follow-up Period (7 days). During the Treatment Period, subjects will have clinic visits for study-related protocol procedures at Day 1, Day 15 and Day 29. The Treatment Period of the study will be considered complete when the last subject completes the last clinic visit.

## **6.2.1.** Schedule of Assessments and Procedures

A comprehensive schedule for assessments and procedures is presented in the SOA (Table 1).

**Table 1:** Schedule of Assessments

				Treatment Period			
	C4 J 1/224	1	2	2	4	=	
_	Study Visit  Visit Day	Screening (-67 to -8)	Pre- Treatment (-7 to -1)	3 Day 1	4 Day 15	5 Day 29 / End of Treatment (EOT)	Day 36 (Follow-up)
Procedure	Visit Window (Days)	N/A	± 2	± 2	± 2	± 2	± 2
Informed consent Verification of er		X X					
Physical examina	•	X					
•							
Review of medic	-	X					
Symptom directed examination 	d physical		X	X	X	X	
Vital signs 		X		X	X	X	
Weight measuren	nent	X	X	X	X	X	
Height measurem	nent 	X					
ECG 		X		X	X	X	
Urinalysis (dipsti		X		X	X	X	
Chemistry blood	collection 	X		X	X	X	
Serum calcium, a phosphorus 	lbumin,			X	X	X	
Cyclic AMP 				X	X	X	
24 hour urine col calcium:creatinin creatinine clearan	e and		X				
Hematology 	)	X		X	X	X	
Coagulation (PT blood collection	and PTT)	X					
PTH (intact)		X					
25-hydroxyvitam	in D level	X					
1,25-dihydroxyvi level	tamin D	X					
Estradiol, FSH		X					
Serum pregnancy		X					
Thyroid stimulati		X					
Urine Drug and A		X		X			
Subject training of administration, or subject diary and of symptoms of le reactions 	ompletion of assessment			X			
Dispensing of cal vitamin D supple	ments		X	X	X		
Study drug admir					tween Visit 3 and	·	
Collect used abal sMTS and swab f drug and swab re	for residual			X	X	X	
BMD of lumbar s hip and femoral r		X					
Investigator asses				X	X	X	

				Treatment Period			
	Study Visit	1	2	3	4	5	6
	Visit Day	Screening (-67 to -8)	Pre- Treatment (-7 to -1)	Day 1	Day 15	Day 29 / End of Treatment (EOT)	Day 36 (Follow-up)
Procedure	Visit Window (Days)	N/A	± 2	± 2	± 2	± 2	± 2
Subject assessme symptoms of loca reaction 				Every day between Visit 3 and Visit 5, inclusive			$X^{23}$
Subject assessment adhesion 	ent of patch			Every day between Visit 3 and Visit 5, inclusive			
Subject assessme	ent of pain 			Every day bet	ween Visit 3 and	Visit 5, inclusive	
Subject assessme errors	ent of user			Every day between Visit 3 and Visit 5, inclusive			
Assessment of su preferences for tr attributes				X X X			
Assessment of su convenience and (TSQM9)				X X			
scale)	sment of subject tability (5-point Likert  X X		X				
	Subject diary review 			X	X	X 	
Document AEs a concomitant med			After signing informed consent until follow up visit				
PK draw 				X	X	X	
Serum marker of metabolism (s-Pl	NP) 			X	X	X	
Drug supply / Dr		_		X	X		
Drug Accountab	ility				X	X	

- 1. A complete physical examination includes a review of the following systems: head/neck/thyroid, eyes/ears/nose/throat, respiratory, cardiovascular, lymph nodes, abdomen, skin, musculoskeletal, and neurological. Breast, anorectal, and genital examinations will be performed when medically indicated. After screening, any clinically significant abnormal findings from the symptom-directed physical examinations should be reported as AEs.
- 2. Including alcohol and tobacco use assessment.
- 3. Blood pressure, pulse rate, body temperature, and respiration rate are to be recorded predose at each study visit. Only blood pressure, pulse rate and respiration rate are to be recorded 1 hour after abaloparatide-sMTS application at each study visit during the treatment period. All blood pressure assessments will be orthostatic. Pulse rate will also be obtained at 15 minutes after abaloparatide-sMTS application at Day 1 (Visit 3), Day 15 (Visit 4) and Day 29 (Visit 5/EOT).
- 4. Height is to be measured at the screening visit/ Visit 1 in the standing position using a medical stadiometer.
- 5. During the Treatment Period, ECGs are to be performed predose after 5 minutes of rest and prior to any blood draw, and 1 hour after abaloparatide-sMTS application on Day 1 (Visit 3), Day 15 (Visit 4) and Day 29 (Visit 5/EOT).
- 6. All routine urinalysis will be performed on a sample freshly voided during the visit and sent to a local laboratory for microscopy if test is positive for micro-organisms via dipstick.
- 7. Blood draw for serum chemistry and hematology will be done during the Screening (Visit 1) and at predose on Day 1 (Visit 3), Day 15 (Visit 4) and Day 29 (Visit 5/EOT).
- 8. Blood draw for serum calcium, albumin and phosphorus will be done at predose and at 4 hours after abaloparatide-sMTS application on Day 1 (Visit 3), Day 15 (Visit 4) and Day 29 (Visit 5/EOT).
- 9. Blood draw for cAMP taken predose and at 30 minutes after abaloparatide-sMTS application on Day 1 (Visit 3), Day 15 (Visit 4) and Day 29 (Visit 5/EOT).
- 10. A 24 hour urine collection will start on Day -8 and complete on the day of the pre-treatment visit (Day -7).
- 11. All subjects will have a urine drug screen for drugs of abuse and alcohol performed on the Screening Period (Visit 1), and on Day 1 (Visit 3).
- 12. When necessary, re-training may be done post Day 1 / Visit 3.
- 13. Study drug is self-administered daily beginning Day 1 (Visit 3) through Day 29 (Visit 5/EOT), inclusive. On Days 1, 15, and 29, subject will self-administer abaloparatide-sMTS at the study site.

- 14. BMD measured by DXA at Screening visit if most recent DXA was done over 12 months prior to screening.
- 15. Investigators will perform an assessment of the application site at each clinic visit prior to application of abaloparatide-sMTS, 5 minutes after application (ie, immediately upon removal of the patch), and 1- hour following abaloparatide-sMTS application. Signs of local skin reactions will be assessed using a 4-point scale, as described in Section 6.6.2.1.
- 16. The subject will maintain a diary to record their assessment of symptoms of local skin reactions for 29 days beginning on Day 1 (Visit 3). The subject will evaluate the application site prior to study drug administration, 5 minutes after application (ie, immediately upon removal of abaloparatide-sMTS), and 1 hour after abaloparatide-sMTS application. Symptoms of local skin reactions will be assessed using a 4-point scale as described in Section 6.6.2.2.
- 17. Subject assessment of patch adhesion immediately prior to abaloparatide-sMTS removal on each day of the treatment period from Day 1 (Visit 3) to Day 29 (Visit 5/EOT).
- 18. An assessment of pain (separate from the pain question on the 4-point scale for local tolerance) will be done after sMTS application.
- 19. The Subject Diary will be reviewed by study personnel at each study visit to ensure subject compliance.
- 20. AEs and SAEs will be recorded on the case report forms starting from the signing of the informed consent until 7 days after the last dose of study medication. All treatment-related AEs will be followed until resolution or stabilization. Any SAEs that occur at any time after completion of the study, which are considered by the investigator to be related to study treatment, must be reported to the Sponsor or its designee.
- 21. Blood samples for measurement of plasma concentrations of abaloparatide will be taken at Day 1 (Visit 3), Day 15 (Visit 4) and on Day 29 (Visit 5/EOT). The pharmacokinetic measurements will be assessed predose and at 10 minutes, 20 minutes, 30 minutes, 1 hour, 1.5 hours, 2 hours, 3 hours and 4 hours after abaloparatide-sMTS application.
- 22. Blood samples for s-PINP taken within 1-hour prior to dosing on Day 1 (Visit 3), Day 15 (Visit 4) and Day 29 (Visit 5/EOT).
- 23. Assessed only for subjects with signs or symptoms of local skin reactions ongoing as of Day 29.
- 24. Subject will return diary to study site.

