## Objectives:

## **Primary:**

• The primary objective of this study is to evaluate the ability of subjects to self-administer abaloparatide-sMTS (300 µg) over a period of 29 days based on pharmacokinetics (PK) and pharmacodynamic (PD) markers.

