## **Treatment Period, Day 1:**

Subjects will be admitted to the clinical research facility on Day 1 of the treatment period. Subjects who continue to meet the study criteria will undergo a symptom-directed physical exam and assessments of vital signs, ECG, updated medical history including concomitant medications, and review of any adverse events (AEs). Other predose assessments include: blood collections for PK, hematology, serum chemistry (including calcium, albumin, and phosphorus), coagulation tests, urinalysis, cyclic adenosine monophosphate (cAMP), and baseline measurements of s-PINP. Urine will be collected for urinalysis and for drug and alcohol testing. The application site will be prepared and cleaned, and predose assessment of the application site will be done by the investigator and the subject.

Immediately before initial dosing (Day 1), the subject will be trained in abaloparatide-sMTS application and instructed how to perform a self-assessment of symptoms of local skin reaction of the application site. After the training, the subject will assess the application site for symptoms of local skin reactions prior to application of abaloparatide-sMTS and will then self-administer the study drug. A subject diary will be provided for recording of user errors in abaloparatide-sMTS application, patch adhesion, and assessment of local tolerance (symptoms of local skin reactions).

Self-assessments of symptoms of local skin reaction will be performed by the subject 5 minutes after application of abaloparatide-sMTS and 1 hour after application of abaloparatide-sMTS on the day of clinic visits. Subject will also be instructed to conduct this assessment of symptoms of local skin reactions, user errors, and an assessment of patch adhesion, beginning Day 1 until Day 29 or end of treatment (EOT) visit.

Investigators will perform an assessment of signs of local skin reaction on the application site prior to abaloparatide-sMTS application, 5 minutes after application (ie, immediately upon removal of abaloparatide-sMTS), and 1 hour after abaloparatide-sMTS application.

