## 2.2. Primary Endpoint

The primary endpoint is the systemic exposure of the drug at Day 1, Day 15 and Day 29.

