Procedure	Visit Window (Days)	N/A	± 2	± 2	± 2	± 2	± 2
Subject training on study drug administration, completion of subject diary and assessment of symptoms of local skin reactions ¹²				X			
Dispensing of calcium and vitamin D supplements			X	X	X		
Study drug administration ¹³				Every day between Visit 3 and Visit 5, inclusive			
Collect used abaloparatide-sMTS and swab for residual drug and swab residuals				X	X	X	
BMD of lumbar spine, total hip and femoral neck by DXA ¹⁴	X						
Investigator assessment of signs of local skin reaction ¹⁵				X	X	X	
Subject assessment of symptoms of local skin reaction ¹⁶				Every day between Visit 3 and Visit 5, inclusive			X ²³
Subject assessment of patch adhesion ¹⁷				Every day between Visit 3 and Visit 5, inclusive			
Subject assessment of pain ¹⁸				Every day between Visit 3 and Visit 5, inclusive			
Subject assessment of user errors				Every day between Visit 3 and Visit 5, inclusive			
Assessment of subject preferences for treatment attributes				X	X	X	
Assessment of subject convenience and satisfaction (TSQM9)					X	X	
Assessment of subject acceptability (5-point Likert scale)				X	X	X	
Subject diary review ¹⁹				X	X	X ²⁴	
Document AEs and concomitant medication ²⁰		After signing informed consent until follow up visit					
PK draw ²¹				X	X	X	
Serum marker of bone metabolism (s-PINP) ²²				X	X	X	
Drug supply / Drug re-supply				X	X		

Procedure	Study Visit	1	2	Treatment Period			6
				3	4	5	
	Visit Day	Screening (-67 to -8)	Pre-Treatment (-7 to -1)	Day 1	Day 15	Day 29 / End of Treatment (EOT)	Day 36 (Follow-up)
Visit Window (Days)	N/A	± 2	± 2	± 2	± 2	± 2	± 2
Drug Accountability					X	X	

1. A complete physical examination includes a review of the following systems: head/neck/thyroid, eyes/ears/nose/throat, respiratory, cardiovascular, lymph nodes, abdomen, skin, musculoskeletal, and neurological. Breast, anorectal, and genital examinations will be performed when medically indicated. After screening, any clinically significant abnormal findings from the symptom-directed physical examinations should be reported as AEs.
2. Including alcohol and tobacco use assessment.

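### Application re-training is permitted just before the Day 15 and Day 29 PK doses with no record required, so a ratio to Day 1 near 1 need not show retained ability to self-administer

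*Protocol*

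**What the plan says.** The synopsis sets the aim: "The primary objective of this study is to evaluate the ability of subjects to self-administer abaloparatide-sMTS" over 29 days, judged on PK and PD markers. Protocol Section 2.2 then ties the primary endpoint to three days: "The primary endpoint is the systemic exposure of the drug at Day 1, Day 15 and Day 29". Table 1, footnote 13 places those doses in the clinic: "On Days 1, 15, and 29, subject will self-administer abaloparatide-sMTS at the study site". Section 5.6 adds that "the Investigator or designee will supervise all study drug administration that occurs at the site", and that at each study visit staff review compliance and "will remind the subject of study drug dosing requirements". Footnote 19 has staff review the diary at each study visit.

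On training, the synopsis says of the first dose: "Immediately before initial dosing (Day 1), the subject will be trained in abaloparatide-sMTS application". For later days the governing text is Table 1, footnote 12: "When necessary, re-training may be done post Day 1 / Visit 3". It is attached to a row marked for Day 1 only, which the SAP's copy of the table gives as "Subject training on study drug administration, completion of subject diary and assessment of symptoms of local skin reactions". The footnote therefore reaches application technique as well as the diary.

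The Pharmacometric Analysis Plan (PAP), Section 9.2.3, compares Days 15 and 29 with Day 1 on log AUC and Cmax, with day as the fixed effect. It does not mention re-training.

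**The concern.** The Day 15 and Day 29 exposures are meant to tell us whether subjects can still apply the patch properly on their own. If a subject whose diary reveals application problems is shown the technique again just before the sampled dose, that profile describes a freshly coached application. The reference has the same character, because the Day 1 dose directly follows training. A ratio near 1 would then be compatible with two quite different situations: technique was retained, or technique slipped and was restored on the day. Nothing in the planned data or analysis would let a reader tell them apart.

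The planned comparison with Cohort 7 of BA058-05-015, where a trained professional applied the product (Protocol Section 1.2), is exposed in the same way, since coaching would move self-application toward that benchmark.

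**Working it through.** The plan gives no alpha, power, margin, error rate or re-training rate, so there is no figure of its own to reproduce. The check is of the text, followed by an illustration under stated assumptions.

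**1. How much of the treatment the primary PK covers.** Of 29 planned daily applications, 3 have PK: 3/29 = 10.3%, all supervised. The other 26 (26/29 = 89.7%) have neither PK nor residual-drug measurement, since Section 6.6.3 limits the latter to patches applied at the site.

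**2. Whether pre-dose re-training is allowed.**
- Footnote 12 permits re-training after Day 1 and sets no time limit.
- Sections 6.2.7.2 and 6.2.7.3 (the Day 15 and Day 29 lists) neither schedule nor bar it.
- Both lists put diary review last, but they are not chronological: Section 6.2.7.3 lists the predose s-PINP sample after self-administration.
- Section 5.3 says later applications follow the Instructions for Use, without ruling out help.
- Section 8.6, on minimising bias, is marked not applicable.

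So it is allowed by omission.

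**3. Whether the analysis would reveal it.** The PAP model contains day only. The PAP has rules for poor adhesion (Sections 9.1.2 and 9.3.3) and a flag for late or early samples (Section 9.3.2), but none for coaching. SAP Section 4.7.8 summarises application success, difficulties, cleaning steps and skin marks; it does not count re-training.

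**4. Illustration of the masking.** Assume n = 18 completers (the planned minimum, from the synopsis). Let k of them have lost technique, each with exposure ratio r to Day 1, and the rest be unchanged at 1. Let m of the k be re-trained before the dose, which restores them fully to 1. The geometric mean ratio to Day 1 is r^((k − m)/n).

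| k | r | none re-trained | half re-trained | all re-trained |
|---|---|---|---|---|
| 2 | 0.25 | 0.857 | 0.926 | 1.00 |
| 2 | 0.50 | 0.926 | 0.962 | 1.00 |
| 2 | 0.75 | 0.969 | 0.984 | 1.00 |
| 4 | 0.25 | 0.735 | 0.857 | 1.00 |
| 4 | 0.50 | 0.857 | 0.926 | 1.00 |
| 4 | 0.75 | 0.938 | 0.969 | 1.00 |
| 6 | 0.25 | 0.630 | 0.794 | 1.00 |
| 6 | 0.50 | 0.794 | 0.891 | 1.00 |
| 6 | 0.75 | 0.909 | 0.953 | 1.00 |

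Example: k = 4, r = 0.5 gives 0.5^(4/18) = 0.857 with no re-training and 0.5^(2/18) = 0.926 with two of the four re-trained. Every k and r here is assumed, and full restoration is the extreme case. The table shows the mechanism, not an estimate for this trial.

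**5. What else speaks to home use.** s-PINP is drawn within the hour before dosing (footnote 22), so same-day coaching cannot alter that day's value. If all doses are taken, the Day 15 sample follows 14 applications, 13 of them at home (Days 2 to 14), and the Day 29 sample follows 28, of which 26 were at home. The daily diary also records user errors and adhesion.

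**The case against.** The strongest reply is that the coaching is inferred. The only further training that the synopsis describes for Days 15 and 29 concerns completing the diary, and it appears there after self-administration. That stands: a reader might infer that the protocol plans technique coaching before the PK dose, and it does not say so. It only fails to prevent it. The pharmacy manual and the Instructions for Use, to which the protocol defers for detail and which were not available, may also regulate the point.

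Section 5.6 is weak evidence of coaching. The reminder sits in a compliance section beside patch counts and missed doses, and may well concern the schedule. Supervising is not coaching either, and clinic dosing is hard to avoid with serial sampling. The case therefore rests on footnote 12.

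A reader might also infer that the design hides a decline in technique. That goes too far. The objective cites PD as well as PK markers, and predose s-PINP and the SAP's by-day application summaries could show a decline at home. They are only partial cover: both are secondary or other endpoints, the diary is self-reported, and SAP Section 4.7.1 defines adherence by splitting s-PINP change at its median, which puts about half the subjects on each side whatever their technique.

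Finally, with no test and no margin (Sections 8.2 and 8.5), there is no defined success criterion toward which the result could be biased. That is right. What is affected is the reading of the ratio, not a decision rule.

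**Conclusion.** The point holds as a gap in the plan. Re-training in application is permitted at any time after Day 1, including just before the Day 15 and Day 29 doses that supply the primary endpoint, and nothing requires it to be recorded. Because Day 1 is also dosed straight after training, a ratio near 1 would not by itself establish retained ability.

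The documents do not support saying that such coaching will occur, how often, or that the Day 15 and Day 29 results will be biased by a given amount. It is tempting to express the effect as clinic exposure over home exposure, but no such contrast is planned, home doses have no PK, and every input would be assumed. The tabulated ratios, 0.63 to 0.97 uncoached against 1.00 fully coached, depend wholly on the assumed k and r and on complete correction.

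For a single-arm, hypothesis-generating Phase 1b study this is a cheap improvement that protects the interpretation of the primary contrast. It does not invalidate the endpoint and has no bearing on sample size.

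**What to change.** - **Order of steps.** In Table 1, footnote 12 (and its copy in the SAP) and Protocol Sections 5.6, 6.2.7.2 and 6.2.7.3, state that on Days 15 and 29 the subject applies the patch from the Instructions for Use before any diary review, technique prompt or application re-training. These follow patch removal, except where staff must step in for safety.
- **Record.** Capture the date, reason and content of every re-training or staff assistance in the eCRF. This also shows for whom the Day 29 result follows re-training given on Day 15.
- **Reporting.** In the PAP, list these records beside the individual PK results and flag any profile taken after same-day, pre-dose coaching.
- **What not to do.** Do not rerun the Day 29 comparison without re-trained subjects as a class. Re-training is likely to be triggered by poor technique, so dropping those subjects removes the ones whose ability lapsed and moves the ratio toward the favourable result.

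The cost is the order of steps at two visits, a small eCRF addition and one listing. The downside is that an application error may be repeated once more before it is corrected.
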